2.3.2.2 Secondary efficacy outcome

Continuous secondary efficacy outcomes are mainly infarct size at 5-7 days after operation and recanalization rate before intervention as well. Analysis for these outcomes will be mainly based on statistical descriptions. Where necessary, analysis of variance or corresponding non-parametric test will be used for between-group comparisons. If applicable, the linear regression analysis will be used with adjustment for the same covariate variables as the primary outcome analysis. When deemed necessary, log or other common transformation of non-normal distribution will be used.

Categorical secondary outcomes include mortality at 90 days after operation, recanalization rate at 24-72 hours, dichotomized mRS score at 90 days after operation (0-1 vs. 2-6, 0-2 vs. 3-6, 0-3 vs. 4-6), successful recanalization before and after Mechanical thrombectomy (MT), and eTICI score at MT final angiography. Chi-square test will be used for comparison between the two groups, or Fisher's exact test will be used for comparison when applicable. The categorical secondary outcomes will be analyzed by logistic or ordered regression analysis to provide a common odds ratio and its confidence interval, if applicable. The adjustment method is the same as that in the primary outcome analysis.

2.3.2.3 Subgroup analysis

Pre-specified subgroup analysis will be performed by examining the interaction between specific baseline characteristics and treatment. Baseline grouping factors for subgroup analysis include, but are not limited to:

- Age
- Baseline NIHSS
- Quartiles of time from onset of symptoms to randomization
- Quartiles of time from onset of symptoms to groin puncture
- Quartiles of time from randomization to groin puncture
- Quartiles of time from onset of symptoms to revascularization
- Quartiles of time from randomization to revascularization
- Ipsilateral extracranial carotid tandem lesion
- Occlusion location
- Collaterals ([Table 9 in Appendix](#))

- Large vessel occlusion due to different etiologies
- Thrombus perviousness
- Thrombus density

See the detailed description of subgroup types and definitions in [Appendix Table 10](#).

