1.1 STUDY DESIGN AND RANDOMIZATION

This is a multicenter prospective randomized clinical trial with open-label treatment and blinded outcome assessment (PROBE). The study will run for 4 years in intervention centers. Randomization will be stratified by center. The treatment allocation is 1:1 for:

- Direct IAT (MT),
- IVT followed by IAT (IVT plus MT)

[figure not shown]

Figure 1 Patient flow in the trial

The intervention group will undergo immediate intra-arterial treatment (IAT) using a stent retriever, as recommended by the steering committee. Patients in the control group will receive alteplase intravenous treatment (IVT) (0.9 mg/kg with a maximum dose of 90 mg), followed by IAT using a stent retriever.

Local application (intra-arterial) of alteplase is allowed in any of the patients included in the DIRECT-MT if necessary. Patients pre-treated with IVT should not receive more than 30mg alteplase during intra-arterial treatment. Delivery of alteplase in shots of 5 mg in 5-10 minutes intervals is recommended. An equivalent dose of 400,000 U urokinase, delivered in shots of 50.000 - 100.000 U, in 5-10 minutes time intervals, is also accepted as escape medication in individual cases. If successful reperfusion (eTICI 2b-3) is not achieved in the direct MT group, IVT with 0.9 mg/kg may be initiated if the 4.5 hour window or maximum dose is not exceeded.

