2.4 DATA PROCESSING CONVENTIONS

2.4.1 Definition of baseline

In this study, baseline values are defined as those data collected before intervention (screening visit). When multiple data collections occur during the baseline period, the final data shall prevail in principle, unless explicitly stated.

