Appendix table 10 Description of Subgroup Types and Definitions

	Subgroups	Number of levels	Levels
1	Age (Years)	3	18-60; 60-80; ≥80
2	Baseline NIHSS	3	2-15; 16-19; ≥20
3	Quartiles of time from onset of symptoms to randomization	4	Min-Quartile 25%; >Quartile 25%-Quartile 50%; >Quartile 50%-Quartile 75%; > Quartile 75% (if applicable)
4	Quartiles of time from onset of symptoms to groin puncture	4	Min-Quartile 25%; >Quartile 25%-Quartile 50%; >Quartile 50%-Quartile 75%; > Quartile 75% (if applicable)
5	Quartiles of time from randomization to groin puncture	4	Min-Quartile 25%; >Quartile 25%-Quartile 50%; >Quartile 50%-Quartile 75%; > Quartile 75% (if applicable)
6	Quartiles of time from onset of symptoms to revascularization	4	Min-Quartile 25%; >Quartile 25%-Quartile 50%; >Quartile 50%-Quartile 75%; > Quartile 75% (if applicable)
7	Quartiles of time from randomization to revascularization	4	Min-Quartile 25%; >Quartile 25%-Quartile 50%; >Quartile 50%-Quartile 75%; > Quartile 75% (if applicable)
8	Ipsilateral extracranial carotid tandem lesion	2	Yes; No
9	Occlusion location	3	ICA; M1; M2
10	Collaterals	2	Grade 0-1; Grade 2-3
11	Large vessel occlusion due to different etiologies	3	Intracranial atherosclerosis; Cardioembolism; Others

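### Four of the five time subgroups are measured after randomisation but are analysed as baseline factors, so their treatment effects and interactions are not randomised comparisons

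*SAP*

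**What the plan says.** Section 2.3.2.3 sets the method: "Pre-specified subgroup analysis will be performed by examining the interaction between specific baseline characteristics and treatment". It introduces the list with "Baseline grouping factors for subgroup analysis include, but are not limited to". Five of the listed factors are times. One, onset to randomization, is fixed at allocation. The other four are not:

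- puncture time counted from stroke onset, given as "Quartiles of time from onset of symptoms to groin puncture";
- puncture time counted from allocation, given as "Quartiles of time from randomization to groin puncture";
- reperfusion time counted from stroke onset, given as "Quartiles of time from onset of symptoms to revascularization";
- reperfusion time counted from allocation, given as "Quartiles of time from randomization to revascularization".

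Appendix table 10 repeats these four as rows 4 to 7, each with four quartile levels, in the same table as age and baseline NIHSS. Section 2.4.1 says that "baseline values are defined as those data collected before intervention (screening visit". Nothing in the SAP marks the four analyses as non-randomised, gives them a separate method, or says where a patient without a puncture or revascularization time belongs.

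**The concern.** A subgroup comparison keeps the protection of randomisation only if the factor could not have been affected by the allocated treatment. These four times can be. The direct arm goes to thrombectomy at once and the control arm receives alteplase first (section 1.1), so puncture time can shift by arm. Reperfusion is a route through which alteplase may act: recanalization before the intervention and the final eTICI score are both secondary outcomes (section 2.1.2.2). Splitting on time to revascularization therefore conditions on something close to an outcome.

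Some patients have no value at all. Section 2.2.2 recognises patients who recover before thrombectomy and are never punctured. Section 1.1 recognises that reperfusion may fail. The proportions can differ between arms.

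At stake is the subgroup table. It could show treatment effects or interactions that do not exist. Within these rows it could also conceal a deficit that runs through reperfusion, which is where omitting alteplase might do harm.

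**Working it through.** **1. Classification.** The SAP gives no figure to reproduce, so the first check is where each time ends.

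| Factor | Ends before or at allocation? | Meets section 2.4.1? |
|---|---|---|
| Onset to randomization | Yes | Yes |
| Onset to groin puncture | No | No |
| Randomization to groin puncture | No (wholly after) | No |
| Onset to revascularization | No | No |
| Randomization to revascularization | No (wholly after) | No |

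So four of the five time factors are post-randomisation.

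**2. A delay in one arm, no treatment effect.** The only SAP input is the assumed control rate of mRS 0-2 in section 1.4: 3% + 9% + 21% = 33%, a logit of about -0.71. Everything else is assumed. Let U be a standard normal prognostic factor, higher meaning worse. Let time T = U + d for controls and T = U for direct thrombectomy. Let logit P(mRS 0-2) = -0.71 - gU in both arms, so the true overall odds ratio is 1.00.

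At a given time T = t, direct patients have U = t and controls have U = t - d. The log odds ratio at that time is then (-gt) - (-g(t - d)) = -gd, so the odds ratio is exp(-gd) and not 1. Pooled quartiles behave almost the same way (simulation of 2,000,000 patients, accurate to about 0.01):

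| d (SD) | g | exp(-gd) | Simulated quartile ORs |
|---|---|---|---|
| 0.3 | 0.3 | exp(-0.09) = 0.91 | 0.91 to 0.94 |
| 0.3 | 0.5 | exp(-0.15) = 0.86 | 0.85 to 0.90 |
| 0.5 | 0.5 | exp(-0.25) = 0.78 | 0.79 to 0.83 |

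Over d = 0.15 to 0.5 and g = 0.3 to 0.5 the quartile odds ratios span about 0.78 to 0.97, all against direct thrombectomy. At d = 0.3 the direct-arm share falls from about 60% in the fastest quartile to about 40% in the slowest. With d = 0 every quartile is at about 1.00.

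**3. A false interaction.** A plain delay shifts all quartiles by a similar amount. If treatment also changes how strongly prognosis drives the time, the quartiles diverge. Take T = wU + noise, with w = 0.3 for direct and 0.7 for control, a control delay of 0.5 residual SD, and U raising the latent outcome by 0.7 per SD. With no treatment effect (overall OR 0.99), the quartile odds ratios are 0.74, 0.85, 0.94 and 1.15. With w = 0 and 0.7 they are 0.60, 0.85, 1.07 and 1.53.

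**4. Patients without a revascularization time.** Assume reperfusion in 85% of controls and 80% of direct patients, with good outcome in 40% if reperfused and 10% if not.

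- Control: 0.85 × 0.40 + 0.15 × 0.10 = 0.355
- Direct: 0.80 × 0.40 + 0.20 × 0.10 = 0.340
- Overall OR: (0.340/0.660) / (0.355/0.645) = 0.936
- Among patients with a time: 40% in both arms, OR 1.00
- Without a time: 0.15 × 318 = 48 controls and 0.20 × 318 = 64 direct

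If these patients are left out, the deficit does not appear in the subgroup rows.

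**The case against.** The contradiction over the word baseline cannot be defended. The case on the other side concerns consequence and remedy.

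- **The delay model gives little interaction.** True: within each scenario of step 2 the quartiles are nearly equal. A false interaction needs the further assumption in step 3. But the spurious within-quartile effects need only the delay.
- **The sizes are upper illustrations.** Step 2 makes all within-arm variation in time prognostic. If half the variance is unrelated to prognosis, the 0.3 SD case shrinks to about 0.91 to 0.96; if 80% is unrelated, to about 0.93 to 0.98. The SAP gives no delay, SD or link between time and prognosis. This stands, and the figures should be read as a mechanism only.
- **Step 4 follows from its inputs and assumes exclusion.** It does, and it models restriction to reperfused patients, not quartiles. Section 2.4.2 lets missing baseline data be imputed by regression, which could be read to cover these times. Imputing a time for an event that never happened would not restore a randomised comparison.
- **Nothing can really be hidden.** Reperfusion outcomes are compared by arm elsewhere in the SAP, and the primary model in section 2.3.2.1 adjusts only for onset-to-randomization time. This limits the harm to the four subgroup rows.
- **Deletion may depart from the protocol.** Section 3 points to a subgroup section in the protocol, which may list these factors. If so, the change has to be logged.

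**Conclusion.** The concern holds. Sections 2.3.2.3 and 2.4.1 cannot both apply to these four factors, and an interaction test on them does not estimate how the treatment effect varies with a patient characteristic. This follows from the design and does not depend on the simulations.

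The size is uncertain. Under the assumed values, a trial with no effect shows quartile odds ratios of about 0.78 to 0.97, nearer 1 if time is only weakly prognostic, and about 1.00 if treatment does not shift the time and does not alter its link with prognosis. The direction in this trial cannot be predicted from the SAP.

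The reach is limited to four subgroup analyses. The primary non-inferiority conclusion and the sample size are not affected. The plan should be changed, but the trial's main result does not depend on it.

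**What to change.** Remove the four bullets from section 2.3.2.3 and rows 4 to 7 from Appendix table 10. Keep onset-to-randomization as the only time subgroup. Report puncture and revascularization times descriptively by arm as process measures, with the number of patients in each arm who have no such time.

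If the sponsor wants to retain the four analyses, the minimum is a separate section that calls them exploratory and non-randomised, drops the baseline label, and states how patients without a puncture or revascularization time are handled.

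The cost is SAP wording and four fewer interaction analyses, plus an entry in section 3 if the protocol lists these subgroups. No data are lost and no new data are needed.

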2.3.2.4 Multiplicity

This study does not consider multiplicity issues and therefore does not adjust significance levels based on multiplicity tests, unless specified otherwise.

2.3.3 Study treatment

2.3.3.1 Intravenous alteplase therapy

Intravenous alteplase therapy will be summarized (only applied to IVT plus MT group), including whether IVT is performed, planned alteplase dose (mg) and residual alteplase volume (ml).

2.3.3.2 Intra-arterial treatment

A descriptive summary of intra-arterial therapy will be provided according to the treatment groups, including anesthesia management, pre-treatment, treatment, eTICI score as determined by final angiography, thrombectomy, intra-operative non-study drugs, stent implantation/balloon dilatation at the intracranial atherosclerosis occlusion site.

2.3.3.3 Digital subtraction angiography (DSA)

The results of DSA will be blindly evaluated by the independent Imaging Committee (Core lab), including but not limited to: ipsilateral extracranial carotid tandem lesion, intracranial arterial occlusions, another occlusion location of anterior circulation except target lesion, arterial occlusive lesion classification (AOL) and intracranial atherosclerosis occlusion, will be summarized according to the treatment groups.

2.3.4 Safety analysis

In this study, the safety analysis will be mainly based on statistical description. All the analyses will be based on PPS.

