1.2 STUDY OBJECTIVES

The primary objective of this trial is to assess the effect of direct IAT compared with IVT followed by IAT, on functional outcome in patients with acute ischemic stroke (AIS), caused by an anterior circulation occlusion that is confirmed by Computed tomography angiography (CTA).

The secondary objective is to explore for superiority of direct IAT relative to IVT followed by IAT.

The tertiary objective is to assess the effect of direct IAT compared with IVT with IAT on neurological recovery (NIHSS), infarct size and occurrence of Symptomatic intracerebral hemorrhage (sICH).

The fourth objective is to collect thrombi and to analyze them with respect to their potential for treatment effect modification.

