2.2 STATISTICAL ANALYSIS POPULATION

The analysis populations include intention-to-treat population (ITT) and per-protocol set (PPS) for this study.

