2.2.2 Per-protocol set

Per-protocol set (PPS) is a subset of ITT, including all randomized subjects who have been treated in the study without major protocol deviations that may significantly impact the interpretation of efficacy results. Detailed protocol deviation criteria will be determined at the latest before database lock. PPS will be used for the primary efficacy outcome and safety analysis. Subjects entering PPS need to satisfy all the following basic criteria:

- (1) Meet all the eligibility criteria specified in the study protocol;
- (2) The subjects were randomized and received the assigned treatment, i.e.
 - No IVT was administered before the intended endovascular treatment (EVT) in the intervention group (direct IAT group);
 - IVT was administered before the intended EVT in patients in the control group.
- (3) Underwent groin puncture, with exception of patients with clinical recovery precluding EVT (due to presumed recanalization before mechanical thrombectomy).

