2.3.2 Analysis of efficacy outcomes

All efficacy data analyses will be based on ITT and for primary endpoint PPS will also be used.

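### Haemorrhage, sICH and SAEs are analysed only on the per-protocol set, which is selected partly on early clinical course; no ITT analysis of these harms is planned

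*SAP*

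**What the plan says.** Two sections of the SAP place safety on the per-protocol set. Section 2.3.4 states "All the analyses will be based on PPS", and section 2.2.2 states "PPS will be used for the primary efficacy outcome and safety analysis".

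No other set is available. Section 2.2 reads "The analysis populations include intention-to-treat population (ITT) and per-protocol set (PPS) for this study". ITT is tied to efficacy: section 2.2.1 makes it the primary efficacy set, and section 2.3.2 says "All efficacy data analyses will be based on ITT and for primary endpoint PPS will also be used".

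Section 2.2.2 sets three basic criteria for the PPS. The first is eligibility. The second is receipt of the assigned treatment sequence, which for controls means "IVT was administered before the intended EVT in patients in the control group". The third is "Underwent groin puncture, with exception of patients with clinical recovery precluding EVT". Further criteria remain open: "Detailed protocol deviation criteria will be determined at the latest before database lock".

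**The concern.** PPS membership is decided by what happens after randomisation, and the third criterion depends on how the patient fares. Among patients who never reach groin puncture, those who improved stay in. Those stopped by haemorrhage, deterioration or death go out. Only the control arm is planned to receive intravenous alteplase before puncture, so losses for early bleeding need not be equal between arms, and this criterion could understate bleeding in the control arm.

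The second criterion can act the other way. It removes controls never given alteplase, who may have had fewer bleeds.

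sICH is part of the tertiary objective in section 1.2, and the trial tests omitting a thrombolytic. Bleeding is therefore central to reading the result, yet its planned by-arm summary leaves out randomised patients. Because the remaining deviation criteria can be settled as late as database lock, when events in an open-label trial have been recorded, the safety denominator is not yet fixed either.

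**Working it through.** **Which population each harm falls under**

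| Outcome | Where it sits in the SAP | Population |
|---|---|---|
| Haemorrhage | Safety outcome (1.3); safety neuroimaging (2.1.3.4, 2.3.4.4) | PPS only |
| sICH | Safety outcome (1.3); SAE class (2.1.3.1) | PPS only |
| SAEs and AESIs | 2.1.3.1, 2.3.4.1 | PPS only |
| Death within 90 days | Secondary efficacy (2.1.2.2, 2.3.2.2) and safety outcome (1.3) | ITT for the comparison; PPS for the safety display |

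The first three rows appear in neither the efficacy variables (2.1.2) nor the efficacy methods (2.3.2), so the ITT rule of 2.3.2 does not reach them.

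**Inputs for an illustration**

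The arm size comes from section 1.4 and can be reproduced: 710 × 0.85 = 603.5; 603.5 / 0.95 = 635.3, rounded up to 636, or 318 per arm. The SAP gives no sICH rate and no exclusion counts, so those below are assumptions.

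**Effect on one arm's rate**

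Let n = 318 and let e be the number of patients with sICH.
- Dropping one event lowers the rate by e/n − (e−1)/(n−1).
- Dropping one event-free patient raises it by e/(n−1) − e/n.
- One dropped event is offset by (n−e)/e dropped event-free patients.

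| Assumed e (rate) | Fall per dropped event | Rise per dropped event-free patient | Break-even |
|---|---|---|---|
| 10 (3.1%) | 0.31 points | 0.01 points | 30.8 |
| 19 (6.0%) | 0.30 points | 0.02 points | 15.7 |
| 29 (9.1%) | 0.29 points | 0.03 points | 10.0 |

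An arm's PPS rate therefore falls below its ITT rate only if the event share among dropped patients exceeds the arm's overall rate.

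Examples starting from 19/318 = 5.97%:
- drop 3 events: 16/315 = 5.08%
- drop 10 event-free patients: 19/308 = 6.17%
- drop 1 event and 20 event-free patients: 18/297 = 6.06%

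**Effect on the comparison of arms**

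Assume equal true sICH counts in both arms (ITT risk ratio 1.00), no exclusions in the direct arm, and exclusions only among controls.
- 19 events per arm; 10 controls excluded, 4 with sICH: the control rate is 15/308 = 4.9%, and the direct/control ratio is (19/318)/(15/308) = 1.23.
- 13 events per arm; 10 controls excluded, 6 with sICH: (13/318)/(7/308) = 1.80.
- 19 events per arm; 30 controls excluded, none with sICH: (19/318)/(19/288) = 0.91.

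Across 13 to 25 events per arm, 5 to 30 excluded controls and 0 to 6 excluded events, the ratio runs from 0.91 to 1.80. Events are few, so a handful of exclusions can move the comparison either way.

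**The case against.** - **Safety is mainly descriptive.** No test or interval for sICH is specified, so the defect lies in the denominator of a by-arm table. That is correct, but readers will compare the arms from that table.
- **Harm is partly covered elsewhere.** Death enters the ITT primary analysis as mRS 6, and 90-day death has its own ITT comparison. Section 4 sends the DSMB mortality and SAE data during enrolment. The point on death stands. The DSMB provision names no population and is not a final analysis, and non-fatal bleeding and SAEs remain uncovered.
- **Review is blinded.** SAEs are adjudicated blind and imaging is read blind by a core laboratory, and settling deviation criteria before lock is common practice. This protects how an event is classified. It does not undo selection of who is counted, and the concern is that these criteria also define the only safety denominator.
- **ITT is not ideal for every harm.** Embolisation during intra-arterial treatment and groin haematoma presuppose the procedure, so an ITT denominator includes patients not at risk. This is a fair refinement and is taken up in the fix.
- **The bias is not demonstrated.** The between-arm ratios rest wholly on assumed exclusions, and the second and third criteria can oppose each other. That is also correct, and no direction is claimed. The case rests on outcome-dependent selection and the absence of any other safety set.

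**Conclusion.** The concern holds. Followed as written, the SAP produces no analysis of haemorrhage, sICH or SAEs by randomised group. It uses instead a set whose groin-puncture criterion depends on early clinical course. The rule is stated in two sections, so it is not a slip in one sentence.

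The size and sign of any bias are unknown. The ratios of 0.91 to 1.80 show sensitivity under assumed event and exclusion counts, with exclusions in the control arm only; they are not predictions. The primary ITT non-inferiority result and the ITT comparison of 90-day death are unaffected. The point should be corrected before database lock because it governs all planned reporting of bleeding harm.

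**What to change.** - In section 2.3.4, name all randomised patients, analysed as assigned (ITT), as the main safety population. In section 2.2.2, remove safety from the stated uses of the PPS.
- Add a supportive table by treatment actually received: intravenous alteplase before EVT, intravenous alteplase only after failed reperfusion (which section 1.1 allows in the direct arm), and none.
- Keep the PPS for safety at most as a sensitivity analysis. Report the number excluded per arm by criterion, and how many of those excluded had sICH or an SAE.
- State that the ITT result is the main one for 90-day death.
- Procedural events, such as embolisation during treatment and groin haematoma, can also be shown among punctured patients.

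The drawback is that ITT includes some controls not given alteplase, which may dilute a difference in bleeding. The table by treatment received addresses this. The cost is SAP wording, the same tables run on another population, and one supportive table, plus the optional display for procedural events. No new data are needed.
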